2.1.3 Statistical Methods

See Section 6.4 for how to identify severe exacerbations.

The proportions of patients with severe exacerbations at each year (p_k , $k=1$ to 5) will be calculated in two ways:

1. Complete Follow-up: using patients who complete the annual follow-up visit or have a follow-up visit (office or phone call) after the visit for that particular year if the annual visit is missed.
2. Complete/Partial Follow-up: using patients who complete the annual follow-up visit no earlier than the start of the follow-up window, have a follow-up visit (office or phone call) after the visit for that particular year if the annual visit is missed, have sufficient follow-up for the year, or had a severe exacerbation during the time period regardless of the amount of follow-up. Sufficient follow-up is having any follow-up visit (office or phone call), adverse event onset date, or hospitalization date that gives the patient at least the number of days of follow-up after the last BT procedure + 42 days given in Table 2.

Table 2. Days for sufficient follow-up by follow-up time

Study Reference Number E7080

Time	Days for sufficient follow-up after the follow-up period starts*
1 Year	337 days
2 Years	702 days
3 Years	1067 days
4 Years	1432 days
5 Years	1797 days

* - the follow-up period starts at last BT procedure + 42 days. The number of days in this column represents the start of the follow-up window after the follow-up period starts and is calculated as # years times 365 days minus 28 days.

All analyses will be done for patients with Complete and Complete/Partial Follow-up. Point estimates and 95% confidence intervals for the proportion of subjects experiencing severe exacerbations during each of the 12-month evaluation periods will be provided. Additionally, the exact upper 95% confidence limit for the difference between the subsequent 12-month proportions and the first 12-month proportion will be calculated, based on methods assuming paired samples; in this analysis, each subsequent 12-month proportion would represent comparisons between the first-year proportion and the second-, third-, fourth-, and fifth-year proportions.

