2.2 Secondary Endpoints

The secondary endpoints will include the following additional safety endpoints which will be evaluated annually through Year 5 following treatment with the Alair System:

- Rates of Severe exacerbations (exacerbations / subject / year)
- Respiratory adverse events* (rates of respiratory adverse events, and proportion of subjects with respiratory adverse events)

Study Reference Number E7080

- Emergency room visits for respiratory symptoms (rates of emergency room visits and proportion of subjects with emergency room visits for respiratory symptoms)
- Hospitalizations for respiratory symptoms (hospitalizations/ subject/ year and the proportion of subjects with hospitalizations for respiratory symptoms)
- Respiratory Serious Adverse Events (detailed narratives will be provided for each event)
- Pre- and post-bronchodilator FEV₁

* A respiratory adverse event is defined as any sign, symptom, illness, clinically significant abnormal laboratory value, or other adverse medical event associated with the “Respiratory System” that appears or worsens in a subject during a clinical study, regardless of whether or not it is considered related to the procedure used as part of the protocol.

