6.4 Identification of Severe Exacerbations (SE)

1. Filter the medication data (MEDS) to keep all courses of oral corticosteroids (CLASS3=OCS) and other medications that are intravenous uses of the same medications - identify those by looking for CLASS3='Other Specify' and lowercase(CLSSP) with values: 'intravenous corticosteriod' 'intravenous corticosteroid' 'cortcosteroid iv' 'corticosteroid iv'. Note there are spelling mistakes in the entered data.
2. Merge the medication data with the AE data by patient and AE related number (RELAENO) on the medication data with AENUM on the AE data.
3. Use the onset date and the resolution date of the AE to determine the length of the SE. If an AE has no resolution date, impute the date of the most recent follow-up (scheduled or

Study Reference Number E7080

unscheduled) as the resolution date. For partial onset and resolution dates, impute dates as described in Section 6.3.

4. When an AE matches with a course of medication, the AE is considered to be an SE, however, when AEs that are SEs occur too close together, the combined AEs are one SE. If the resolution date of one AE selected as an SE is \leq 6 days before the onset date of another AE that is an SE, then combine the AEs into one SE. There could be more than two AE combined into a single SE.
5. SEs are classified in the time period where the onset date of the SE occurs regardless of the duration of the SE.
6. For each time period, count the number of SEs for each patient and whether the patient has an SE or not. Two types of summaries will be done for the SEs (also ER visits and hospitalization) to include the following patients: (1) patients with the follow-up visit or later visit for that time period, and (2) patients from (1) and patients with any SE in the time period.

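### SAP 6.4 step 6 picks patients for the ER-visit and hospitalization summaries by severe exacerbation, so some early leavers with a respiratory ER visit or admission fall in neither summary

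*SAP*

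**What the plan says.** SAP 2.2 lists among the secondary safety endpoints, evaluated annually, "Hospitalizations for respiratory symptoms (hospitalizations/ subject/ year and the proportion of subjects with hospitalizations for respiratory symptoms"; ER visits for respiratory symptoms are listed in the same way. SAP 2.2.2 says these are summarised descriptively and names no denominator.

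The only rule on who is counted for them by year is in SAP 6.4, step 6: "Two types of summaries will be done for the SEs (also ER visits and hospitalization) to include the following patients". The first set is given as "1) patients with the follow-up visit or later visit for that time period". The other set, which enlarges the first, is given as "2) patients from (1) and patients with any SE in the time period". Step 4 of the same section defines the event that admits an early leaver: "When an AE matches with a course of medication, the AE is considered to be an SE". Step 1 limits those courses to oral corticosteroids and intravenous use of the same drugs.

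SAP 2.1.3 states that all analyses will use two sets, Complete and Complete/Partial Follow-up. The second is wider than set 2 of step 6. It also admits a patient with an "adverse event onset date, or hospitalization date that gives the patient at least the number of days of follow-up" required for that year. It admits a patient who "had a severe exacerbation during the time period regardless of the amount of follow-up", but gives no such exemption for an ER visit or a hospitalization.

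**The concern.** Patients are selected for a named safety endpoint by whether they had a different outcome. A subject who leaves during the year contributes to the ER and hospitalization summaries only through an SE. If the respiratory ER visit or admission had no linked steroid course, the subject drops out of both summaries along with the event.

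Leaving could be related to the event. Protocol 6.8 lets the investigator withdraw a subject for possible harm from continuing, for needing treatment the study does not allow, or for serious new illness including lung disease. Nothing in the plan tests the effect on these endpoints: the tipping-point analysis in SAP 2.1.3 and 6.3 covers the primary endpoint only.

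The completer denominator in the protocol sits in section 6.3, the primary analysis. Protocol 6.4, on the secondary analyses, sets no such restriction. Longer-term safety is part of the study's stated objective, so these yearly figures will be read as safety results.

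**Working it through.** **Stated figure reproduced.** The thresholds in SAP Table 2 are "calculated as # years times 365 days minus 28 days". For k = 1 to 5, 365k − 28 gives 337, 702, 1067, 1432 and 1797 days, as printed.

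**Rules applied to four Year 1 cases.** Days run from the start of follow-up. Phone contacts are taken to count as visits in step 6, as they do in 2.1.3.

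| Case | Step 6 set 1 | Step 6 set 2 | 2.1.3 Complete/Partial |
|---|---|---|---|
| Pneumonia admission day 150, no linked steroid, death day 160 | out | out | out (160 < 337) |
| Same admission on day 345, death day 350 | out | out | in (at least 337) |
| Asthma admission day 150 with linked intravenous steroid, death day 160 | out | in | in |
| Pneumonia admission day 150, annual visit missed, phone contact day 450 | in | in | in |

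The first case is the gap, and it exists under both sections. The second shows that step 6 and 2.1.3 disagree; the 2.1.3 route helps only patients followed to within 28 days of the end of the year.

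**Size, on assumed inputs.** The documents give no yearly hospitalization proportion for this study. The minimum enrolment of 250 and the 20% loss over 5 years come from SAP 2.1.2; spread evenly, that is 250 × 0.20 / 5 = 10 leavers a year, so 240 stay. The 4% of stayers hospitalized, and p = 8%, 15% or 25% of leavers hospitalized before leaving, are assumptions.

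- Set 1: 240 × 0.04 / 240 = 9.6/240 = 4.0%.
- All subjects: (9.6 + 10p)/250 = 4.16%, 4.44%, 4.84%. The gap is 0.16, 0.44 and 0.84 percentage points, or about 4%, 10% and 17% of the all-subject figure.
- If p is also 4%, the all-subject figure is 10.0/250 = 4.0% and there is no gap.
- Hospitalized leavers absent from set 1: 0.8, 1.5 and 2.5.

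Set 2 depends on the share s of hospitalized leavers who had an SE that year: (9.6 + 10ps)/(240 + 10ps). At p = 15%, where the all-subject figure is 4.44%:

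- s = 0: 9.6/240 = 4.0%.
- s = 0.5: 10.35/240.75 = 4.3%.
- s = 0.8: 10.8/241.2 = 4.5%.

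Non-hospitalized leavers with an SE would add to the denominator and lower these slightly.

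**The other reading of set 2.** If the SE condition is meant as the event being summarised, every hospitalized leaver enters and no event-free leaver does: (9.6 + 10p)/(240 + 10p) = 4.3%, 4.6%, 5.0%, against 4.2%, 4.4%, 4.8% in all subjects. Set 2 is then slightly high.

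**Wider range.** With 11 of 250 or 15 of 300 leaving in a year, and 6% to 40% of leavers hospitalized, none with an SE, the number in neither set runs from 11 × 0.06 = 0.7 to 15 × 0.40 = 6.0 a year.

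**The case against.** The case for leaving step 6 alone has several sound parts.

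- **The affected group is narrow.** Any adverse event linked to an oral or intravenous steroid course makes an SE under step 4, not only an asthma event, so a steroid-treated admission enters set 2. Set 1 keeps anyone with a later visit. The gap needs no linked steroid, no annual visit and no later visit together. This stands.
- **The events are reported elsewhere.** SAP 4.6 tabulates adverse events by year, with seriousness, for anyone with at least one post-treatment visit, and Table 3 moves pneumonia into the respiratory class. Respiratory serious events get narratives, and the safety board reviews respiratory hospitalizations (Protocol 8.1). A reader might infer that admissions vanish from safety reporting; the documents do not support that. These outputs still do not replace the endpoint. An ER visit without admission need not be serious, and Protocol 8.1 reports stays under 24 hours as serious events without counting them as hospitalizations.
- **The direction is not fixed.** A reader might infer that both summaries flatter the device by 4% to 17%. Those figures describe set 1 on assumed rates. Set 2 can be close to the all-subject figure, and under the other reading it errs slightly high, so that in this illustration the two sets bracket that figure.
- **Leavers are not shown to be hospitalized more often.** Protocol 6.8 makes it plausible, no more.
- **Nothing formal depends on these endpoints.** SAP 2.2.1 sets no hypothesis for them. This limits the weight of the point but does not make the rule right.

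**Conclusion.** The point holds on the literal text of step 6. A subject with a respiratory ER visit or admission, no steroid-linked adverse event that year, and no visit at or after the annual visit is in neither summary. SAP 2.1.3 recovers only those followed to within 28 days of the year's end, and the two sections conflict on who is counted. Neither ITT as the primary set (SAP 3.1) nor the general statement in SAP 6.3 that all enrolled patients are eligible for evaluation overrides the narrower rule.

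What is distorted is the yearly rate and proportion for two descriptive secondary safety endpoints. The primary endpoint and the adverse event tables are outside this point. The effect is probably small: under the assumptions above, 0.2 to 0.8 percentage points in set 1, and the same in set 2 only if no leaver hospitalized that year had an SE. The documents do not allow a firmer figure. Nor do they exclude person-time from the rate; they simply do not state its denominator.

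**What to change.** In SAP 6.4 step 6, take ER visits and hospitalizations out of the SE sets and give them their own rule:

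- Include every treated subject who enters the year.
- Report rates as events divided by person-years observed in that year, to last contact or death.
- Report proportions as a time-to-first-event estimate at 365 days that handles early leavers, and state how death is treated. SAP 6.3 already provides for methods for censored data.
- Keep the completer summary as supportive.
- Reconcile step 6 with SAP 2.1.3, so that one definition says who is counted in a year and whether a hospitalization date establishes follow-up.

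Adding to set 2 only the leavers who had the event would not be enough, because it pushes the proportion upward.

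The cost is one SAP paragraph and modest programming. ER visits and hospitalizations are asked about at every quarterly contact (Protocol 6.7 and 7.3.12), SAP 2.1.3 already uses hospitalization dates, and Protocol 6.8 requires status at last contact for subjects lost to follow-up. The downside is that the figures may be slightly less favourable.

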6.5 Medication Dose Conversions

Table 4. Beclomethasone Equivalents

Drug	Conversion Factor
Budesonide	1.25
Fluticasone	2
QVAR	2.5
Mometasone	2.5
Triamcinolone	0.5
Flunisolide	0.5
Ciclesonide	2.5

Table 5. Salmeterol Equivalents

Drug	Conversion Factor
Formoterol	100/24
Formoterol Fumarate	100/24

7 REVISION HISTORY

Document Revision Number	Template Number and Version	Section	Change	Reason for Change
AA	NA	All	First version	
AB	90702621, AC	All	
• Reorganized SAP to match the standard template (90702621)• Replaced sections 2-4 from version AA with a protocol summary• Changed the primary statistical analysis for the primary endpoint to be paired instead of a two-group test• Update the algorithm for identifying severe exacerbations to be more specific• Add Table 3 to describe the reassignment of SOCs	The original SAP was written by a CRO (QST) before BSC took over statistical support for this study; the SAP was re-written to conform to the current SAP template and to update statistical methods for the primary endpoint.
